Study Protocol and Statistical Analysis Plan:

Evidence of the Advantages of Preoperative Intra-aortic Balloon Pump in Surgical Revascularization of Acute Myocardial Infarction

Brief Title: Use of Intra-aortic Balloon Pump Before Surgery for Acute Myocardial Infarction

NCT number: NCT06468982

Document date: May 1, 2021

Evidence of the Advantages of Preoperative Intra-aortic Balloon Pump in Surgical Revascularization of Acute Myocardial Infarction

Patients hospitalized due to acute myocardial infarction (AMI) and scheduled for coronary artery bypass grafting (CABG) surgery based on the decision of the Cardiology and Cardiovascular Surgery council will be included in this prospective observational cohort study. Based on their clinical conditions, the patients will be categorized into two groups: Group A, comprising those receiving intra-aortic balloon pump (IABP) support, and Group B, comprising those not receiving IABP support.

The patients' anamnesis, medical history, physical examination findings, laboratory results, and EuroScore-II scores will be meticulously recorded. Details of the assessments are as follows:

Assessment of Chest Pain (Angina): Chest pain severity will be evaluated on the first day of admission using a scoring system based on the Wong-Baker FACES® pain scale (0–10; Wong-Baker FACES Foundation; https://wongbakerfaces.org). For patients in the IABP group, pain severity will also be recorded immediately before IABP placement and at 12 and 24 hours post-implantation.

Laboratory Studies: The following parameters will be analyzed: hemoglobin (g/dL), hematocrit (%), platelet count, troponin (ng/mL), CK-MB (U/L), LDL (mg/dL), C-reactive protein (CRP, mg/L), glycated hemoglobin (HbA1c, %), and creatinine (mg/dL). High-sensitivity cardiac troponin I (hsCTI) levels will be measured, with the reference range of 0–0.04 ng/mL for both genders, as per our hospital's laboratory standards. hsCTI levels will be checked at admission and subsequently every 24 hours for both groups until the patient undergoes surgery.

Echocardiography (ECHO): On the first day, ECHO will be performed to assess ventricular function, ejection fraction (EF%), valve pathologies, and any ventricular abnormalities such as aneurysm or ventricular septal rupture. Follow-up ECHO will be conducted during the early postoperative period and at the first-month follow-up after discharge to reassess EF% and identify any pericardial effusion.

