Patients who demonstrate a decline in hsCTI levels or experience recurrent chest pain attacks will undergo coronary artery bypass grafting (CABG). All surgical procedures will be performed by the same surgical team using a standardized approach. Surgical Approach: The surgeries will be conducted via a median sternotomy under cardiopulmonary bypass (CPB). Complete revascularization will be achieved with the application of an aortic cross-clamp (ACC), guided by the vascular anatomy identified during angiography. Assessment of Graft

Flow: Following the removal of the ACC and the termination of CPB, transit-time flow measurement (TTFM) will be employed to evaluate the graft flow rates, ensuring optimal surgical outcomes.

In the postoperative period, the following parameters will be recorded: Mechanical Ventilation Duration (MV): Measured in hours from the patient's admission to the intensive care unit (ICU) until the cessation of mechanical ventilation. Bleeding Volume: The total amount of bleeding in milliliters during the first 24 hours postoperatively. Length of Stay in the Intensive Care Unit (ICU): The duration (in days) from the postoperative phase until the patient is transferred to the general ward. Total Length of Hospital Stay (HS): The number of days from hospital admission to discharge. Low Cardiac Output Syndrome (LCOS): LCOS will be defined as the presence of the following criteria: Requirement for high-dose positive inotropic agents (e.g., adrenaline, dobutamine, or noradrenaline) administered via continuous infusion, lactic acidosis (lactate levels >4 mmol/L), persistent hypotension and decreased or absent urine output. In-Hospital Mortality: Any death occurring within 30 days postoperatively will be classified as in-hospital mortality.

Exclusion criteria

To ensure a homogeneous distribution of risk factors between the groups and to accurately evaluate the effect of IABP on troponin levels, the following patients will be excluded from the study:

• Patients requiring emergency surgery due to iatrogenic cardiac or coronary injuries caused by angiography.

• Patients with mechanical complications of acute myocardial infarction, such as chordae rupture or ventricular septal rupture.

• Patients undergoing surgery using the off-pump or pumped beating heart method.

- Patients with peripheral arterial disease.
- Patients with renal failure.
- Patients with a history of cerebrovascular accidents.

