- · Patients presenting with acute cardiogenic shock or cardiac arrest

Preoperative IABP Application and Indications:

The primary indications for intra-aortic balloon pump (IABP) application in patients include elevated troponin levels and recurrent or persistent chest pain at rest.

Other common indications are:

- Hemodynamic instability.
- Multivessel coronary artery disease.
- Left main coronary artery disease.
- Narrow and/or tortuous coronary artery anatomy where percutaneous coronary intervention (PCI) has failed or is not feasible.

Procedure:

The IABP catheter is typically inserted into the femoral artery by cardiovascular surgeons under local anesthesia. The placement of the catheter is confirmed either in a hybrid operating room or using a portable imaging scope.

Statistical Analysis

The research will be conducted utilizing IBM SPSS 24 (IBM, Armonk, NY, USA) software and R-project version 4.2.3 for statistical analysis. The statistics will be provided in terms of mean, standard deviation, median, minimum, maximum, percentage, and count. After testing for normality, baseline characteristics of the two groups will be compared using Student's t-test or the Mann–Whitney U-test for continuous variables and chi-square or Fisher's exact tests for categorical variables. Differences between the IABP group and the control group regarding repeatedly measured outcomes will be analyzed using mixed ANOVA. The prognostic value of risk factors for in-hospital mortality will be evaluated by multivariate logistic regression analysis. The propensity score will be computed using a logistic regression model, incorporating the following covariates: age, gender, creatinine, CK-MB, hs-CTI levels, preoperative LVEF, and EuroScore II. The statistical significance level will be set at p<0.05.

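### Hemodynamic instability is an IABP indication, yet it is undefined, has no stated boundary with the excluded shock, and is not a separate propensity-score covariate

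*Combined protocol and SAP*

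**What the plan says.** All references are to the combined protocol and SAP.

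- **Exclusion criteria.** The exclusions serve two purposes: "To ensure a homogeneous distribution of risk factors between the groups and to accurately evaluate the effect of IABP on troponin levels". One of them is "Patients presenting with acute cardiogenic shock or cardiac arrest". It is tied to presentation. No criterion for shock and no time of screening is given.
- **Preoperative IABP Application and Indications.** This section first gives the main reasons for a balloon: "The primary indications for intra-aortic balloon pump (IABP) application in patients include elevated troponin levels and recurrent or persistent chest pain at rest". A second list, introduced by "Other common indications are", includes "Hemodynamic instability", with no threshold or definition.
- **Opening paragraph.** Allocation is not randomised: "Based on their clinical conditions, the patients will be categorized into two groups". The comparator is "Group B, comprising those not receiving IABP support", so it is defined by not receiving a balloon and not by having no indication for one.
- **Statistical Analysis.** A logistic propensity model uses age, gender, three laboratory values (creatinine, CK-MB, high-sensitivity troponin), preoperative ejection fraction and EuroScore II. The section does not say whether the score is for matching, weighting, stratification or adjustment, and it describes no check of overlap.

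**The concern.** Instability plays two roles in this plan. If it is severe enough at presentation to be called shock, the patient leaves the study. If it is less severe, it is a listed reason for a balloon and hence for membership of Group A. No measured criterion separates the two, and the propensity model has no term for this stated driver of treatment.

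Two consequences follow. First, if unstable patients receive IABP more often than stable ones, Group A carries more baseline risk, and part of any excess in mortality or low cardiac output syndrome would be charged to the balloon. Second, with no criterion and no screening time, the shock label could be applied after the IABP decision is known. Exclusion would then depend on treatment, and the result could move in either direction.

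**Working it through.** The document gives no sample size, event rate, allocation ratio or count of unstable patients, so there is no planned figure to reproduce. The check has a reading step and an illustration.

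**1. The boundary.** The plan does define hemodynamic compromise after surgery: low cardiac output syndrome is set out through inotrope need, lactate above 4 mmol/L, persistent hypotension and reduced urine output. Nothing comparable exists before surgery. Physical examination findings are recorded, but no blood pressure or inotrope item is named, and the Laboratory Studies list has no lactate.

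**2. Timing.** One exclusion, surgery off-pump or on a beating heart, depends on the operation performed. Eligibility is therefore not shown to close before the IABP decision.

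**3. Adjustment.** None of the seven propensity covariates is a direct measure of hemodynamic status. The document does not list the components of EuroScore II, so it cannot show whether that score carries the information.

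**4. Size, under assumed inputs.** None of these comes from the document:

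- share of enrolled patients who are unstable but not in shock, p = 10%, 20%, 30%
- probability of IABP if stable, s = 40%
- probability of IABP if unstable, q = 40% to 100%
- mortality 15% if unstable and 5% if stable
- no effect of IABP

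Formulas:

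- size of Group A: A = p·q + (1 − p)·s; size of Group B: 1 − A
- unstable share: u_A = p·q / A; u_B = p·(1 − q) / (1 − A)
- mortality in a group: 0.05 + 0.10·u
- crude OR = odds in Group A / odds in Group B

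Low end, p = 0.10 and q = 0.50: A = 0.05 + 0.36 = 0.41. u_A = 0.05/0.41 = 12.2% and u_B = 0.05/0.59 = 8.5%. Mortality is 6.2% against 5.8%, OR 1.07.

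High end, p = 0.30 and q = 1: A = 0.30 + 0.28 = 0.58. u_A = 0.30/0.58 = 51.7% and u_B = 0. Mortality is 10.2% against 5.0%, OR 2.15.

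| IABP if unstable (q) | Unstable share of Group A, p = 10% to 30% | Unstable share of Group B, p = 10% to 30% | Crude OR, p = 10% / 20% / 30% |
|---|---|---|---|
| 40% (same as stable) | 10.0% to 30.0% | 10.0% to 30.0% | 1.00 / 1.00 / 1.00 |
| 50% | 12.2% to 34.9% | 8.5% to 26.3% | 1.07 / 1.11 / 1.12 |
| 70% | 16.3% to 42.9% | 5.3% to 17.6% | 1.21 / 1.34 / 1.41 |
| 90% | 20.0% to 49.1% | 1.8% to 6.7% | 1.38 / 1.65 / 1.83 |
| 100% | 21.7% to 51.7% | 0% | 1.47 / 1.84 / 2.15 |

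The direction is the same whenever q exceeds s. The size depends strongly on q, and so does the number of comparable patients in Group B. These are crude odds ratios. How much the planned score would remove cannot be computed.

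**The case against.** The strongest defence is that the two entries are compatible. Excluding shock and arrest at presentation while enrolling lesser instability is coherent, and it removes some of the most extreme patients. It does not create the imbalance. Homogeneity is also only one of two stated purposes; the other concerns troponin. This stands: there is no contradiction between the lists, only a missing boundary.

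A reader might also infer that every unstable patient is either dropped or given a balloon, leaving almost none in Group B. The document does not support that. The indications are called common, not mandatory. Group B is simply everyone without a balloon. Elevated troponin and multivessel disease are also listed as indications, and both are likely to be frequent in a cohort with infarction scheduled for bypass, yet a group without IABP is still planned. The list does not read as a fixed assignment rule, and no counts are given.

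Nor does it follow that modelling cannot recover the comparison. A propensity score is planned, and some of its covariates may be correlated with instability. Failure is certain only where overlap is absent, which is unknown. Finally, labelling shock according to treatment is a possibility that the wording leaves open. Nothing in the text suggests that it is intended.

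What survives is narrower: a stated driver of treatment is undefined, has no explicit term in the adjustment, and comes with no check of whether the groups overlap on it.

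**Conclusion.** The point holds as a gap in definition and adjustment. Group A may hold more unstable patients than Group B. The shock exclusion reduces the problem at its extreme but does not secure the homogeneity that is its stated aim, and the plan would not reveal how much imbalance is left.

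Under the assumed inputs, the spurious crude odds ratio runs from 1.07-1.12 when half of the unstable patients receive IABP to 1.47-2.15 when all do. It would be 1.00 if instability did not influence the decision, but listing it as an indication makes that unlikely. The upper range is the no-overlap extreme and should not be read as the expected bias. Confidence is moderate, because the deciding quantity, the probability of IABP given instability, is not in the document. The matter should be settled before analysis and does not by itself invalidate the study.

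**What to change.** 1. Reconcile the exclusion and indication entries for study purposes, so that it is clear in measured terms which unstable patients are in the study. The clinical content of that boundary is for the investigators.
2. Apply the shock exclusion at one fixed time, the council decision and before any IABP, in the same way to all patients.
3. Record routine hemodynamic values (blood pressure, lactate, inotrope use) for every patient at that time.
4. Add this pre-IABP status to the propensity model and state how the score will be used.
5. Report balance and overlap by group, with standardised differences, and limit the comparison to the region of overlap.
6. As a sensitivity analysis, report the comparison restricted to patients who were stable at that time.

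These steps govern who is compared and how, not who receives a balloon. The unstable patients stay in the main comparison wherever counterparts exist; excluding them all would narrow the study's question.

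The cost is protocol wording, a few more recorded values and one or more extra model terms. Where overlap is poor, the conclusion will apply only to the patients who can be compared. One limit remains: a status fixed at the council decision does not capture patients who become unstable afterwards and then receive a balloon. Because group is defined by receipt of IABP, they will count in Group A, and their number should be reported.

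### The exclusions cannot make the groups homogeneous, balance is checked only by baseline significance tests, and the propensity score has no balance diagnostic and no link to the outcome analysis

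*Combined protocol and SAP*

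**What the plan says.** The opening paragraph describes a prospective observational cohort and forms the groups without randomization: "Based on their clinical conditions, the patients will be categorized into two groups". Under Preoperative IABP Application and Indications, the primary indications "include elevated troponin levels and recurrent or persistent chest pain at rest". Haemodynamic instability, multivessel disease and left main disease are listed as further indications.

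The Exclusion criteria section gives two purposes for the exclusions: "To ensure a homogeneous distribution of risk factors between the groups and to accurately evaluate the effect of IABP on troponin levels".

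The Statistical Analysis section says that, after normality testing, "baseline characteristics of the two groups will be compared using" t-tests or Mann–Whitney tests for continuous variables, with chi-square or Fisher tests for categorical variables. It adds: "The statistical significance level will be set at p<0.05". Between-group differences in repeatedly measured outcomes go to a mixed ANOVA, for which no covariate is named. In-hospital mortality goes to a multivariable logistic regression whose covariates are not listed. A propensity score is computed by logistic regression from age, gender, creatinine, CK-MB, hs-CTI, preoperative LVEF and EuroScore II. The section does not say whether the score is used for matching, weighting, stratification or adjustment, or how balance is examined afterwards. No sample size is given.

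**The concern.** Exclusions that apply equally to both groups narrow the population. They do not equalize the characteristics that decide who receives a balloon pump. Here those characteristics are markers of severity, and one of them, troponin, is also the quantity on which the effect of IABP is to be evaluated.

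A significance test is a poor instrument for judging the remaining imbalance, because its p-value mixes the size of the imbalance with the number of patients. The propensity score could help, but as written it is calculated and then left unused: no diagnostic shows whether it balances its covariates, and no outcome analysis includes it. At stake is whether a difference between the IABP and control groups can be attributed to IABP at all.

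**Working it through.** **Inputs.** From the plan: significance level 0.05 (two-sided assumed), non-random grouping, seven score covariates. Not in the plan and therefore assumed: group sizes, allocation ratio (1:1), size of imbalance, and correlation of covariates with the outcome. The plan has no design figure to reproduce.

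**Step 1: what the baseline tests miss.** For a true standardized mean difference (SMD) d and n per group, the t statistic is noncentral t with 2n − 2 degrees of freedom and noncentrality d × √(n/2). The chance of a non-significant test is the probability that it lies within ± the 97.5% t quantile. For d = 0.3, the noncentrality is 0.3 × √25 = 1.5 at n = 50, 0.3 × √50 = 2.12 at n = 100 and 0.3 × √100 = 3.0 at n = 200.

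| True SMD | n = 25 | n = 50 | n = 100 | n = 200 |
|---|---|---|---|---|
| 0.2 | 89% | 83% | 71% | 49% |
| 0.3 | 82% | 68% | 44% | 15% |
| 0.4 | 72% | 49% | 20% | 2% |
| 0.5 | 59% | 30% | 6% | 0.1% |

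The largest observed SMD that still gives p ≥ 0.05 is the t quantile × √(2/n): 0.57, 0.40, 0.28 and 0.20 at n = 25, 50, 100 and 200. The same imbalance therefore passes or fails according to n.

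**Step 2: what an unadjusted comparison does.** Suppose there is no IABP effect and k independent confounders, each with SMD d in the same direction and correlation r with the outcome. The bias in outcome SD units is k × r × d. A simulation of 8,000 runs per scenario, with an unadjusted t-test on one outcome, gave:

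| k, d, r | n | Bias (SD) | All baseline tests non-significant | False effect, all runs | False effect, given all non-significant | Both together |
|---|---|---|---|---|---|---|
| 1, 0.3, 0.5 | 50 | 0.15 | 67.4% | 11.8% | 6.4% | 4.3% |
| 1, 0.3, 0.5 | 100 | 0.15 | 43.9% | 18.4% | 7.1% | 3.1% |
| 3, 0.3, 0.4 | 50 | 0.36 | 31.8% | 43.2% | 17.4% | 5.6% |
| 3, 0.3, 0.4 | 100 | 0.36 | 8.8% | 71.6% | 30.1% | 2.6% |
| 5, 0.2, 0.4 | 50 | 0.40 | 40.0% | 51.5% | 25.7% | 10.3% |
| 5, 0.2, 0.4 | 100 | 0.40 | 18.4% | 80.5% | 45.4% | 8.4% |

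Two things follow. Several modest imbalances can produce a false effect with no baseline test flagging any of them. And most false effects occur when at least one baseline test is significant: with three confounders at n = 50, 43.2 − 5.6 = 37.6% of runs. For those the plan states no consequence, so the missing link between score and outcome analysis matters at least as much as the missed tests.

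The scenarios are illustrations. Three confounders at r = 0.4 explain 3 × 0.16 = 48% of outcome variance, and five explain 80%, which is strong.

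**Step 3: how strict an SMD limit can be.** With no true imbalance, an observed SMD has a standard deviation of about √(2/n): 0.20 at n = 50 and 0.14 at n = 100. The chance that it exceeds 0.10 in absolute value is P(|Z| > 0.5) = 62% and P(|Z| > 0.71) = 48%. A fixed limit of 0.10 on every baseline variable would be triggered by chance alone about half the time or more at these sizes.

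**The case against.** The plan is not blind to confounding. Its score includes LVEF, hs-CTI and EuroScore II, and a multivariable mortality model is planned. Means, standard deviations and counts will be reported, so a reader could work out most SMDs. This stands as a limit on the criticism, but an unused score and an uncomputed SMD do not protect the comparison.

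Four stronger readings are tempting, and the documents do not support them.

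- A reader might infer that p > 0.05 will be taken as proof of homogeneity. No such rule is written; the plan says only that the groups will be compared.
- A reader might infer that the tests will usually miss a relevant imbalance. That depends on unstated group sizes: a 0.3 SD imbalance is missed in 15% of studies at 200 per group, and 0.5 SD in 6% at 100. Because troponin and pain drive assignment, their imbalance may be large and easily detected.
- A reader might infer that one undetected imbalance is enough to create an IABP effect. For a single linear confounder the outcome shift is r × d, smaller than the imbalance itself. After a non-significant baseline test, a false effect appeared in 6.4% of runs at 50 per group with d = 0.3 and r = 0.5, close to the nominal 5%.
- A reader might object that p-values after matching rise merely because patients are dropped. That is true in general, but the plan does not mention matching.

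**Conclusion.** The point holds in a limited form. The exclusion rationale claims more than exclusions can deliver under assignment by indication. The only comparability check is one whose answer depends on an unstated sample size. The propensity score is left without a diagnostic or a stated use. If the plan is followed literally, the repeated-outcome comparison is unadjusted and open to confounding. Its size cannot be fixed from the documents: the illustrations give a bias of 0.15 SD for one modest confounder and 0.36 to 0.40 SD for three to five acting in the same direction. They assume 1:1 groups, independent linear confounders and a single unadjusted outcome test in place of the mixed ANOVA.

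**What to change.** - Report SMDs for the baseline variables before and after applying the score, alongside or instead of the p-values.
- Judge balance by SMD for the score covariates and for prognostic or indication variables outside the score, such as admission chest pain and left main or multivessel disease (capture coronary anatomy as a baseline variable if it is not already on the form). A value of 0.10 can serve as a guide, but not as a hard trigger for every laboratory value.
- State how the score is applied, and use it in the between-group outcome analyses, including the analysis of repeated measurements. Where a prognostic variable stays imbalanced, re-specify the score or adjust for that variable in the outcome model, whatever its p-value.
- Reword the exclusion rationale to say that the exclusions restrict the population, not that they ensure homogeneous groups.

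The cost is SAP wording and one more table. The baseline comparison may look less favourable, and a small sample will limit how many covariates the outcome model can carry, so the prognostic variables should be ranked in advance.

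### Risk factors for 30-day death are to be modelled by unpenalised logistic regression with no expected death count or sparse-event rule; a Firth fit of the same multivariable model is safer if deaths are few

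*Combined protocol and SAP*

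**What the plan says.** All references are to the combined protocol and SAP.

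- **Method (Statistical Analysis).** "The prognostic value of risk factors for in-hospital mortality will be evaluated by multivariate logistic regression analysis". No predictor list, number of terms, selection rule, penalised or exact method, or plan for separation follows. I read this as ordinary maximum likelihood, the default when nothing else is named.
- **Outcome (postoperative parameters).** "Any death occurring within 30 days postoperatively will be classified as in-hospital mortality".
- **Covariates (Statistical Analysis).** The only list is "age, gender, creatinine, CK-MB, hs-CTI levels, preoperative LVEF, and EuroScore II". It belongs to the propensity score, and no use of that score is described. IABP is not said to be in the mortality model.
- **Population (Exclusion criteria).** Mechanical complications, renal failure, peripheral arterial disease and previous cerebrovascular accident are excluded, as are "Patients presenting with acute cardiogenic shock or cardiac arrest".
- **Size.** Patients "will be included in this prospective observational cohort study", but no sample size, mortality rate or expected number of deaths is given.
- **Software.** SPSS 24 and R 4.2.3 are named.

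**The concern.** What a logistic model can support depends mainly on the number of deaths, not the number of patients. Nothing in the plan ties the model to the deaths. If few patients die, one predictor or a combination of predictors may separate deaths from survivors completely. Maximum likelihood then has no finite solution. Where a solution exists, sparse data can push odds ratios away from 1 and leave standard errors unreliable.

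At stake is whether the mortality model gives a usable result at all, and whether the odds ratios it yields overstate the risk factors. Because IABP is not a stated term, the model could also be run without addressing the exposure in the study title.

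**Working it through.** **1. Figure to reproduce.** There is none, because the document states no sample size, deaths, mortality or number of terms. Everything below rests on assumed values.

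**2. Expected deaths.** Deaths = N x p. Deaths per term are shown for an assumed 8 terms (IABP plus seven covariates borrowed from the propensity list).

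| N | p = 2% | p = 5% | p = 10% |
|---|---|---|---|
| 100 | 2 (0.25 per term) | 5 (0.62) | 10 (1.25) |
| 200 | 4 (0.5) | 10 (1.25) | 20 (2.5) |
| 400 | 8 (1.0) | 20 (2.5) | 40 (5.0) |
| 1000 | 20 (2.5) | 50 (6.25) | 100 (12.5) |

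The binomial probability of 10 or fewer deaths at p = 5% is 0.99 for N = 100, 0.58 for N = 200 and 0.009 for N = 400. Plausible sizes therefore fall on both sides of the point where trouble starts.

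**3. Simulation A.** It used 600 data sets per setting, eight true predictors, about 40% on IABP and a true IABP log OR of -0.50. A fit counts as failed if there were no deaths, separation or no convergence. Both columns fit the same 8 terms, so only the penalty differs.

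| Mean deaths (N, p) | ML: failed / mean log OR / SD | Firth: failed / mean log OR / SD |
|---|---|---|
| 3 (100, 3%) | 68.3% / -0.53 / 1.59 | 3.8% / -0.38 / 1.11 |
| 5 (100, 5%) | 38.3% / -0.48 / 1.55 | 0.8% / -0.37 / 1.02 |
| 10 (100, 10%) | 8.8% / -0.60 / 1.15 | 0.0% / -0.49 / 0.88 |
| 10 (200, 5%) | 7.5% / -0.69 / 1.05 | 0.0% / -0.55 / 0.79 |
| 20 (200, 10%) | 0.2% / -0.56 / 0.61 | 0.0% / -0.48 / 0.53 |
| 20 (400, 5%) | 0.3% / -0.54 / 0.57 | 0.0% / -0.48 / 0.51 |
| 80 (800, 10%) | 0.0% / -0.52 / 0.28 | 0.0% / -0.50 / 0.27 |

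Means and SDs are over estimable fits only.

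- *Bias of ML at about 10 deaths:* (0.60 - 0.50)/0.50 = 20% and (0.69 - 0.50)/0.50 = 38%. The Monte Carlo standard errors are 1.15/sqrt(547) = 0.049 and 1.05/sqrt(555) = 0.045. The first excess is about 2 standard errors and the second about 4, so the direction is clearer than the size.
- *Bias of ML at about 20 deaths:* 0.04/0.50 = 8% to 0.06/0.50 = 12%.
- *Firth failures:* the rates of 3.8% and 0.8% are close to the chance of no deaths at all, 0.97^100 = 4.8% and 0.95^100 = 0.6%. No method can estimate an odds ratio from such data.
- *Firth shrinkage:* at about 5 deaths (0.50 - 0.37)/0.50 = 26% towards no effect; at about 20 deaths (0.50 - 0.48)/0.50 = 4%.

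**4. Penalty or fewer terms?** With two terms (EuroScore II and IABP), ML still failed in 42.7% at about 3 deaths, 16.7% at about 5 and 1.8-2.5% at about 10. Two-term Firth failed in 3.8%, 0.8% and 0%, the same as 8-term Firth. The penalty, more than the term count, restores estimability.

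**5. Remaining uncertainty.** Ratio of upper to lower 95% limit = exp(2 x 1.96 x median SE). For 8-term Firth at about 5 deaths this is exp(3.92 x 0.94) = 40; at about 10 deaths it is 15 to 20. For two-term Firth it is 91 at about 3 deaths and 45 at about 5.

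**6. Simulation B.** A separate simulation used 4 to 8 terms and a true log OR of -0.69. ML failed in about 2-25% over roughly 5 to 10 deaths. At about 5 deaths Firth with the same terms cut failures from 20-25% to under 1%. At about 10 deaths the mean log OR was -0.78 with ML (0.09/0.69 = 13% too far from zero) and between -0.64 and -0.70 with Firth. At 20 to 40 deaths Firth still had slightly less bias and a smaller SD.

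**The case against.** Three stronger readings are tempting, and the documents support none of them.

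- **That only a handful of deaths is likely.** The document gives no figure for this. The exclusions remove several high-risk groups, but every patient has an acute infarction, and the IABP indications still include hemodynamic instability, left main disease and multivessel disease. With 20 or more deaths the planned method would serve almost as well.
- **That an overfitted eight-term model is planned.** The seven covariates are listed for the propensity score, in a separate sentence. The number of terms in the mortality model is unstated, so overfitting cannot be shown from the text.
- **That a two-term model of IABP plus the propensity score should replace the planned one and would be stable.** It would swap the stated prognostic aim for a treatment association, and reporting the other factors one at a time would leave them unadjusted for each other. With 3 to 5 deaths a two-term Firth interval still spans a 91- to 45-fold range. The penalty does most of the work in any case.

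It can also fairly be said that the failure rates depend on invented covariate effects: the two simulations differ (20-25% against 38% at about 5 deaths). Nor is exaggeration uniform: in simulation A the mean ML log OR at about 5 deaths was -0.48 against -0.50, though only among the 62% of data sets that could be fitted.

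These objections make the harm conditional. They do not remove the omission: the plan has no expected deaths, no predictor list and no rule for sparse events.

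**Conclusion.** The point holds in conditional form. The plan names an unpenalised logistic model for 30-day death and provides nothing that matches it to the number of deaths. With about 5 to 10 deaths and 4 to 8 terms, failed fits are common (about 2-25% or, with 8 terms, 8-38%, depending on the simulation). At about 10 deaths the mean log odds ratio was exaggerated by about 13% to 38%. At about 20 deaths or more, failures were 0.2-0.3% and bias was modest.

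These sizes rest on assumed N, mortality, number of terms, covariate effects and IABP share; none comes from the document. The preference for Firth is less sensitive to them. With the same terms it failed far less often when deaths were few, had a smaller SD, and lost almost nothing when deaths were plentiful. It does not create information, and a result from few deaths remains imprecise. This is a cheap improvement that should be made, not a flaw that invalidates the study.

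**What to change.** Amend the mortality paragraph of the Statistical Analysis section as follows.

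1. State the expected sample size and number of 30-day deaths, with the basis for each.
2. Keep the multivariable prognostic model, but fit it by Firth-penalised logistic regression with profile-likelihood confidence intervals in R.
3. Include IABP as a term. List the other predictors in advance in order of priority, and state how the observed number of deaths limits how many enter, without looking at their association with death.
4. State a death count below which the result is labelled exploratory. About 20 is a reasonable starting point, since the two fits came close there with 8 terms.
5. Optionally, add a separate Firth model of death on IABP plus the propensity score for the treatment association. It should supplement the prognostic model, not replace it.

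The cost is SAP wording, as R is already named. The downsides are that odds ratios are shrunk somewhat (slightly at 20 deaths, more at about 5), that fewer factors can be claimed as independent predictors, and that intervals stay very wide when deaths are few.
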